Daily Habits & Consumer Preferences Study Protocol with SAP

December 23, 2025

Study Protocol

Objectives

Over 70% of U.S. adults are classifiable as overweight or obese, and weight stigma, defined as the negative attitudes, prejudice, and discrimination directed at heavier individuals, is highly prevalent. Our long-term goal is to understand and ultimately mitigate the negative behavioral effects of weight stigma that pose risk for obesity and cardiovascular disease. In order to achieve this goal, we must first gain a fundamental understanding of the causal processes of weight stigma and how it functions in people's lives to promote obesity. Therefore, the focus of this basic experimental study in humans (BESH) is to use an experimental manipulation as a probe in order to gain a fundamental causal understanding of the obesogenic nature of weight stigma. Much of the available evidence tying weight stigma to poor health outcomes is observational, precluding conclusions regarding causality. The few existing experimental studies that can infer causality only assess immediate outcomes in artificial lab settings. Moreover, the literature has thus far focused on documenting the negative effects of weight stigma, without attending to resilience factors that could confer protection against them.

Therefore, our overall objectives are to (1) test the central hypothesis that weight stigma causes decrements in health behaviors in everyday life using ecological momentary assessment (EMA) and actigraphy, and (2) identify resilience factors that could, in future work, be targeted in weight stigma interventions. The central hypothesis is based on existing literature and our 8 preliminary studies, which include a study of 2,000 participants census-matched to U.S. population demographics demonstrating associations between greater weight stigma and binge eating and sleep disturbance. Our focus on health behaviors is important because behaviors account for 40% of preventable deaths and are strongly protective against obesity and cardiovascular disease. Moreover, there is evidence that the COVID-19 pandemic is detrimentally impacting diet, exercise, and sleep. Using a true experimental design, we will therefore pursue the following

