aims that capitalize on our deep experience manipulating weight stigma in laboratory experiments and our demonstrated expertise in ecological momentary assessment and actigraphy studies. This research will provide a fundamental understanding of weight stigma to potentially identify a future intervention target to ameliorate unfavorable health consequences for the hundreds of millions of Americans at risk for weight stigma, obesity, and cardiovascular disease.

Aim 1: Test the causal effects of weight stigma on diet, physical activity, and sleep in everyday life—we will randomly assign participants to a weight stigma vs. control manipulation and measure changes health behaviors in their everyday lives (3-day diet as captured by EMA food diaries, objectively measured physical activity captured by 24-hour actigraphy, and sleep, captured objectively by overnight actigraphy and subjectively self-reported sleep measures).

Aim 2: Identify resilience factors that confer protection against the causal effects of weight stigma—we will test moderators drawn from two sources of theory (identity/belongingness and stress/coping).

Design

Our approach consists of a one-way between-subjects experimental design, randomizing participants to weight stigma vs. control. We will measure immediate effects on objective eating behavior, and in addition engage in EMA to measure diet, physical activity, and sleep using actigraphy for 3 days pre- and post-manipulation.

Methods

Inclusion criteria are as follows [with justification in brackets]: (1) Age 18 and older [because children do not largely make their own diet/eating choices]; (2) BMI 28 or above [because heavier individuals are those who are most at risk for weight stigma and our preliminary data demonstrate our manipulation is effective in those with BMI 28 or higher]; (2) English-speaking [as the interaction task takes place in English]. Exclusion criteria include: (1) Recent (<1 year) diagnosis of major mental disorders including any eating disorder, mood disorder, schizophrenia, or PTSD [because weight stigma manipulations may impose undue risk for those with these conditions]; (2) Recent (<1 year) diagnosis of major physical conditions that limit physical movement [in order to avoid floor effects due to lack of physical activity]; (3) Recent (<1 year)

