diagnosis of sleep disorder [in order to avoid ceiling effects due to disrupted sleep]; (4) Allergy to any of the foods in the food buffet [to guard participant safety].

Recruitment strategies will consist of a variety of methods including online postings, some targeted to specific demographics to match our planned enrollment table (for example, Facebook offers specification of populations for ads to reach), physical flyers around the UCLA community, listings on clinicaltrials.gov, clinicaltrials.ucla.edu, and other study recruitment portals such as researchmatch.com, and the psychology subject pools for our university. We have found in the past that recruiting to match the demographics of LA County is not difficult for White, Asian, and Latinx populations. However, recruiting 9% African American participants may be a challenge. Therefore, we will activate our existing database of churches and beauty salons/barber shops that enabled us to successfully recruit a 50% African-American sample in a prior study funded by the Robert Wood Johnson Foundation. We will also conduct in-person recruitment at community centers and events in areas represented by a large proportion of ethnic/racial minority individuals.

The cover story for this study will be that we are studying the relationship between health habits and consumer preferences. This cover story ties together the disparate elements of the study, including the health behavior measurement and taste test task. All participants will be scheduled between 3:00 and 5:00 pm. This time frame was chosen because we want the manipulation to occur late in the day to be proximal to sleep, but not so late that dinnertime hunger levels create ceiling effects for eating.

All participants will provide written, informed consent. Eligibility will be confirmed by measuring potential participants' weight and height in the lab. The other inclusion/exclusion criteria will be confirmed through a questionnaire. Participants will complete the resilience measures. They will then be given instructions on actigraph use and will affix the physical activity actigraph to their leg (the sleep actigraph is a wrist device that they will put on like a normal watch before sleep). They will also be trained on the food diary, along with serving size estimation training [1], [2]. To ascertain that the participants have successfully understood how

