Descriptive statistics will be generated for the demographic, mediating, and outcome variables, in aggregate and by randomized assignment (weight stigma vs. control). Eating behavior is often skewed, and if kilocalorie intake evinces skew greater than 3.0 we will conduct transformations (either square root or natural-log) to normalize the data. In addition, all other variables with skew greater than 3.0 will be natural-log transformed. Cronbach's α will be computed to confirm internal consistency for self-reported outcomes. Values will be averaged over the 3 pre- and post-manipulation days, respectively. With this randomized study, intention to treat analysis will be performed to ensure causal inference. Analysis of variance will test main effects of the weight stigma manipulation on the outcome measures. As we are utilizing randomization, we do not anticipate a priori that covariates will be necessary. However, we will test for potential failure of randomization and include necessary covariates in the models.

Moderation analyses to test resilience buffering will be conducted using the PROCESS macro, Model 1 [24], testing whether the effect of the weight stigma condition on the three outcomes is moderated by the resilience variables. We will additionally control for exposure-outcome (e.g., socioeconomic status, operationalized as recommended by the MacArthur Network on SES and Health [25]) and moderator-outcome (e.g., depression, measured by the Center for Epidemiologic Studies Depression Scale [26]) confounding. As we are engaging in primary data collection in the laboratory, missing data will occur at relatively low levels in our experience. However, in consultation with Co-I/Biostatistician [name], we will use missing data/imputation methods if necessary.

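### Aim 2 moderation: controlling for depression as a main effect does not protect the condition × resilience interaction; add a condition × depression sensitivity regression beside Model 1

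*Combined protocol and SAP*

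**What the plan says.** The moderation paragraph of the Statistical Analysis Plan names PROCESS Model 1, which has one product term (condition × moderator), for "testing whether the effect of the weight stigma condition on the three outcomes is moderated by the resilience variables". It then adds two kinds of covariate control. SES comes under the first: "We will additionally control for exposure-outcome (e.g., socioeconomic status" (the parenthesis continues with the measure). Depression comes under the second: "moderator-outcome (e.g., depression, measured by the Center for Epidemiologic Studies Depression Scale [26]) confounding". The paragraph does not state the functional form of either covariate, when either is measured, or whether any condition × covariate product is fitted. No sensitivity analysis of the moderation result appears elsewhere.

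Aim 2 is worded as "Identify resilience factors that confer protection against the causal effects of weight stigma", and the Objectives want to "identify resilience factors that could, in future work, be targeted in weight stigma interventions". In Methods, the resilience factors are measured at the first visit, before the manipulation ("Participants will complete the resilience measures"). They are not randomized. The exclusion criteria remove people with "Recent (<1 year) diagnosis of major mental disorders including any eating disorder, mood disorder, schizophrenia, or PTSD".

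**The concern.** Condition is randomized, so a main effect of depression mostly reduces noise. The weak point is the moderator, which is only observed. People high on a resilience factor may also be less depressed, and low depression may be what blunts the stigma effect. A depression main effect lets the average outcome vary with depression, but it does not let the stigma effect vary with depression. Any such variation is then picked up by the only product term in the model, condition × resilience.

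The plan itself identifies depression as a confounder of the moderator, yet the control it appears to intend does not reach the coefficient being tested. At stake is the interpretation of a positive Aim 2 result: a factor could be credited with protection, and put forward as a future target, when depression explains the pattern.

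**Working it through.** **Inputs from the documents.** The analysed N is 300 and recruitment is 330 (300 + 30 for about 10% dropout, which reproduces as 300 × 1.10). Allocation is equal. There are six resilience measures and three outcomes. The plan gives no figure for this bias to reproduce, and the Table 2 values are not in the available text.

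**Assumptions, none in the documents.** Standardised variables, residual SD 1, two-sided 5% level, and a stigma effect of 0.3 SD. On that scale g = 0.075, 0.15 and 0.30 SD mean that the effect changes by 25%, 50% and 100% per SD of depression.

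**Size of the shift.** Write depression as D = rM + u, where M is resilience. Then condition × D = r(condition × M) + condition × u. Leaving out a term with coefficient g therefore moves the condition × M coefficient by r × g. At r = −0.5 and g = 0.15 this is −0.075 SD; at g = 0.30 it is −0.15 SD.

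**Rejection rate with no true buffering.** The SE of the interaction is about 2/√300 = 0.115, and 0.117 in simulation. The rate is about Φ(−1.96 + |rg|/SE) + Φ(−1.96 − |rg|/SE). For r = −0.5 and g = 0.15, 0.075/0.117 = 0.64, so the rate is Φ(−1.32) + Φ(−2.60) = 0.093 + 0.005, about 10%. Simulation of Model 1 with depression and SES as main effects gives:

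| \|r\| | g = 0.075 | g = 0.15 | g = 0.30 |
|---|---|---|---|
| 0.1 | 5.0% | 5.1% | 5.5% |
| 0.2 | 5.4% | 5.6% | 7.7% |
| 0.3 | 5.4% | 6.6% | 11.7% |
| 0.4 | 5.7% | 8.1% | 17.0% |
| 0.5 | 6.1% | 9.8% | 24.4% |

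With g = 0 or r = 0 the rate is about 5%. With condition × depression added, it is about 5% in every cell and the mean shift is about zero, whether or not condition × SES is also included.

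**Effect of the exclusion.** If excluding recent mood disorder removed the top 10% of depression scores (assumed), the bottom row would become 6.0%, 7.4% and 15.6%. Removing the top 20% would give 5.8%, 7.1% and 12.5%.

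**SES.** If SES were the only modifier and correlated 0.3 with resilience (assumed), Model 1 would reject in 5.3% and 6.7% of trials for a 25% and a 50% change per SD.

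**Precision of the added model.** With depression alone correlated with resilience, the SE grows by 1/√(1 − r²): 1.05, 1.15 and 1.25 at |r| = 0.3, 0.5 and 0.6. If SES also correlates 0.3 with resilience and −0.3 with depression, and condition × SES is included, the SE goes from 0.117 to 0.126, 0.138 and 0.148, about 8%, 18% and 27%. In that case, power for a true 0.3 SD moderation is about Φ(0.3/SE − 1.96). That gives 73% for Model 1 and 66%, 58% and 53% for the added model; simulations agree within about two points.

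**Noise in the comparison.** With no rival effect, the difference between the two estimates has a chance SD of about 0.04 at |r| = 0.3 and 0.07 at |r| = 0.5. The shifts to be seen at g = 0.15 are 0.045 and 0.075, about the same size.

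**The case against.** The strongest reply is that Model 1 does what the plan literally asks: it tests whether the stigma effect differs by resilience. The Objectives leave the targeting of a factor to future work. That stands. The case rests on Aim 2's wording about protection and on the plan's own statement that moderator-outcome confounding will be controlled.

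The size depends on two assumed quantities, and for |r| up to 0.3 and g up to 0.15 it is under two percentage points. Group identification, one of the six moderators, may hardly correlate with depression. This also stands.

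The comparison between models discriminates poorly. Taking 25% shrinkage as an example, among significant Model 1 results at g = 0.15 only about a quarter (|r| = 0.3) to a half (|r| = 0.5) of false buffers shrink that much, while about 12% of true buffers do so by chance at |r| = 0.5. This rules out a shrinkage threshold or an automatic change of wording. It does not rule out showing both estimates.

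The SES term is weakly motivated. The plan lists SES as exposure-outcome confounding, which randomization handles in expectation.

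A reader might go further and infer that the Aim 2 test is invalid, or that its false-positive rate is a quarter or more. The documents do not support that. They give neither r nor g; 24% needs |r| = 0.5 together with a doubling or abolition of the stigma effect per SD of depression; and the mood-disorder exclusion may narrow the range. Nor do they say that covariates enter only as main effects. That is the natural reading of control within a one-product model, not a stated rule.

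**Conclusion.** The point holds as a cheap improvement, with medium confidence. If depression enters as a main effect, the stated control does not do its job for the claim that a resilience factor confers protection. The interaction shifts by about r × g, which is modest for modest values and nil if either is zero. The rejection rates in the table count as errors only when the result is read as protection by the factor itself. As evidence that the stigma effect differs across levels of resilience, Model 1 stands. Depression is the main issue and SES is secondary. Nothing here changes the analysed 300 or the recruited 330.

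**What to change.** Keep Model 1 as the planned test and state how its covariates enter. For each moderator and outcome, pre-specify one sensitivity regression: the Model 1 terms plus condition × depression, with the CES-D taken before the manipulation, as the resilience measures are. Condition × SES may be added to the same model as a secondary term, with SES also measured beforehand. Report the condition × resilience estimate and 95% CI from both models side by side, with the condition × covariate estimates. Set no shrinkage rule and do not require significance in the added model. State instead that Model 1 alone shows effect modification, and that attributing protection to the factor will be discussed in light of both estimates.

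The cost is a few sentences and at least 6 × 3 = 18 extra regressions on variables already planned. The drawbacks should be stated too:
- The added model has a wider interval and lower power, as shown above.
- The change between models is noisy.
- Only measured covariates are covered, and measurement error leaves some bias. At r = −0.5 with an assumed reliability of 0.8, the added model still shifts by −0.020 SD (g = 0.15) or −0.039 SD (g = 0.30), against −0.075 and −0.15 in Model 1.
- It may over-adjust if depression lies on the pathway from resilience.

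For these reasons it belongs beside Model 1, not in its place.
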